2 STUDY OBJECTIVES

2.1 Primary objective

The primary objective is to compare the horizontal and vertical changes in osseous dimension of a single bound edentulous zone following guided bone regeneration. Three different bone augmentation techniques will be used. Data will be obtained from DICOM images acquired by CBCT imaging. The dimensional location of the facial bone plate in the Z-axis and Y-axis will be reported in terms of a reference point (the mid-alveolar point positioned on a tangent drawn from the cementoenamel junctions of the mesial and distal adjacent teeth. The changes from baseline to six months will be compared.

Hypothesis: The treatment group with GUIDOR membrane with allograft is superior to comparative treatment groups (GUIDOR membrane alone or Bio-Gide® membrane with allograft).

2.2 Secondary objectives

Secondary objectives of the study are to evaluate and compare:

- Presence or absence of soft tissue inflammation within 3mm from the incision line
- Presence or absence of infection
- Membrane exposure
- Soft tissue complications, including wound dehiscence

3 STUDY PLAN AND PROCEDURES

3.1 Overall study design and flow chart

[figure not shown]
The study is designed as a randomized control prospective study with multiple study centers and is a physician initiated study.

The study population will consist of individuals requiring guided bone regeneration prior to dental implant therapy in a single, bound edentulous zone. Sites within zone 14-24 or 34-44 (maxillary and mandibular first premolars and anterior teeth) will be included.

60 subjects will be included at two centers. Each subject will be randomized into one of three groups: group A (GUIDOR® membrane and FDBA), group B (GUIDOR® membrane alone) and group C (Bio-Gide® membrane and FDBA). Each center will enroll 30 subjects, 10 per group.

The study will be a 6 month follow-up with 7 main clinic visits.

Figure 1 Study flow chart

Visit 1: Screening

Subjects in need of guided bone regeneration of a single bound edentulous site prior to dental implant surgery that are deemed eligible by meeting inclusion and exclusion criteria will be considered for treatment in this study. The single edentulous zone must lie within the region 14-24 or 34-44 (maxillary or mandibular first premolar or anterior tooth).

Before any assessment or examination is carried out for study purposes the subject must have been informed orally and in writing about the study, and have signed the appropriate consent forms. The informed consent process will be given in accordance with Declaration of Helsinki 2008 and 21 CFR Part 50. Informed consent for the research study will be given and signed on paper, as well as HIPAA authorization. All subjects for this study will be provided with a patient information sheet describing this study and providing sufficient information for subjects to make an informed decision about their participation in this study. The subject will have an opportunity to ask the Investigator questions to obtain a better understanding of the study and its procedures. Then, the formal consent of the subject, using the IRB-approved consent form, will be obtained before that subject undergoes any study procedure.

Written informed consents must be obtained prior to any examination carried out for study purposes.

Individuals meeting all inclusion and none of the exclusion criteria and that have signed all appropriate consent forms will be further evaluated. Screening will entail evaluation of general dental and systemic health. It will also include a clinical and radiographic assessment of the edentulous site and the adjacent teeth. Pre-existing radiographs (e.g. panoramic and intraoral) can be used but must not be older than 6 months. Subjects with adequate alveolar ridges will immediately be scheduled for Visit 2 provided that they fulfill all inclusion and none of the exclusion criterion.

The following items will be completed during the screening visit:

- Medical, Social, and Dental History
- Oral examination
- Concomitant Medications Use: Concomitant medications which will be collected during this study consist of prescription and OTC drugs except for dietary supplements.
- Confirm radiographic assessment for inclusion and exclusion criteria

Visit 2: Cone Beam Computed Tomography Imaging (2 weeks \pm 4 days from Visit 1)

Small field-of-view cone beam computed tomography (CBCT) imaging will be obtained for all patients at baseline and 6 months following the guided bone regeneration surgical procedure using the Carestream CS9300 System or equivalent system. Images will provide baseline data for horizontal and vertical bone locations. CBCT imaging will be conducted in accordance to institutional standards and technique.

Visit 3: Guided Bone Regeneration Surgery (8 weeks \pm 7 days from Visit 1)

[figure not shown]
Prior to randomization, confirmation and verification of all inclusion and exclusion criteria must be completed.

The time of enrollment for this study is defined at the time the patient signs the informed consent form, meets all inclusion criteria and no exclusion criteria, is randomized and receives study treatment.

Randomization and Stratification

Subjects meeting all inclusion and none of the exclusion criteria will be randomly allocated to group A, B or C. The randomization will be per center and based on smoking status.

Figure 2 Randomization and stratification

Pre-Surgical Procedures

Buccal and crestal photographs of the planned surgical site will be obtained using a Canon 50D digital camera body with a Canon 100mm f/2.8 macro lens and a Canon MR-14EX macro ring flash or equivalent device. The films must be stored in the subject's medical chart.

Pre-surgical antibiotic prophylaxis will be provided for patients at risk for infective endocarditis or with total joint replacement according to current guidelines provided by the American Dental Association, American Heart Association, and the American Academy of Orthopaedic Surgeons (9, 10).

Surgical Procedure

Sedation options will be discussed with the patient and a decision will be made to have:

- No sedation
- Oral conscious sedation

Anesthesia:

20% benzocaine topical anesthesia will be maintained for 1 minute. Infiltration anesthesia using 2% lidocaine with 1:100,000 and 2% lidocaine with 1:50,000 epinephrine will be provided. It is anticipated that 3.6 to 5.4cc will be used.

The product will be implanted according to the Instruction for Use. A crestal incision will be placed in the bound edentulous site with sulcular incisions extending to the distal line angles of the adjacent teeth. Vertical releasing incisions using a papilla sparing design will be extending to or beyond the mucogingival junction.

A full-thickness mucoperiosteal flap will be elevated and extended to permit access to the edentulous site requiring bone augmentation. Periosteal release with a new #15 blade and bone decortication of the edentulous site with a 1/4 round bur will be completed.

Bone graft material and barrier membranes will be placed within the confines of the adjacent osseous architecture accordingly:

- Group A: FDBA reconstituted in saline will be used to augment the edentulous site and will be covered by a GUIDOR® membrane.
- Group B: A GUIDOR® membrane will be placed over the edentulous site.
- Group C: FDBA reconstituted in saline will be used to augment the edentulous site and will be covered by a Bio-Gide® membrane.

Following completion of bone augmentation, the flaps will be reapproximated and primary closure will be achieved using 5-0 (CV-6) ePTFE suture in the areas of the crestal and sulcular incisions and 5-0 chromic gut suture in the areas of the vertical releases. It is anticipated that horizontal mattress, vertical mattress, continuous interlocking, and/or simple loop sutures will be employed.

Post-Surgical Procedures

Post-surgery, infiltration anesthesia with 0.5% bupivacaine with 1:200,000 will be provided. It is anticipated that 1.8cc will be used.

Post-surgical antibiotic coverage will be provided to patients. It is recommended that a 7-day course of 500mg Amoxicillin every 8 hours or 300mg Clindamycin every 6 hours will be provided.

Post-surgical analgesics will be provided, it is recommended that 800mg Ibuprofen every 6-8 hours and 5/325mg Acetaminophen/Hydrocodone every 4-6 hours.

The following will be completed and documented post-surgery:

- Buccal and crestal photographs of the surgical site will be obtained using a Canon 50D digital camera body with a Canon 100mm f/2.8 macro lens and a Canon MR-14EX macro ring flash or a similar product. The photographs will be stored in the subject's medical history and chart.
- Concomitant medication changes
- Adverse event assessment
- Subject instructions on post-surgical care per institutional standard of care

Visit 4: Post-Operative Visit (7 days ± 2 days post guided bone regeneration procedure)

The following will be completed and documented:

- Surgical site examination: The surgical site will be examined for inflammation within 3mm of the incision line. The site will also be assessed for membrane exposure, wound dehiscence, and infection.
- Buccal and crestal photographs of the surgical site will be obtained using a Canon 50D digital camera body with a Canon 100mm f/2.8 macro lens and a Canon MR-14EX macro ring flash or a similar product. The photographs will be stored in the subject's medical history and chart.
- Concomitant medication changes
- Adverse event assessment

Visit 5: Post-Operative Visit (14 days \pm 2 days post guided bone regeneration procedure)

The following will be completed and documented:

- Surgical site examination: The surgical site will be examined for inflammation within 3mm of the incision line. The site will also be assessed for membrane exposure, wound dehiscence, and infection.
- Suture material removal
- Buccal and crestal photographs of the surgical site will be obtained using a Canon 50D digital camera body with a Canon 100mm f/2.8 macro lens and a Canon MR-14EX macro ring flash or a similar product. The photographs will be stored in the subject's medical history and chart.
- Concomitant medication changes
- Adverse event assessment

Visit 6: Post-Operative Visit (28 days \pm 2 days post guided bone regeneration procedure)

The following will be completed and documented:

- Surgical site examination: The surgical site will be examined for inflammation within 3mm of the incision line. The site will also be assessed for membrane exposure, wound dehiscence, and infection.
- Buccal and crestal photographs of the surgical site will be obtained using a Canon 50D digital camera body with a Canon 100mm f/2.8 macro lens and a Canon MR-14EX macro ring flash or a similar product. The photographs will be stored in the subject's medical history and chart.
- Concomitant medication changes
- Adverse event assessment

Visit 7: Post-Operative Visit: Cone Beam Computed Tomography Imaging (24 weeks \pm 7 days post guided bone regeneration procedure)

The following will be completed and documented during this visit:

- CBCT: Small field-of-view cone beam computed tomography (CBCT) imaging will be obtained for all patients using the Carestream CS9300 System. Images will provide post-augmentation data for horizontal and vertical bone locations.
- Surgical site examination: The surgical site will be examined for inflammation within 3mm of the incision line. The site will also be assessed for membrane exposure, wound dehiscence, and infection.
- Buccal and crestal photographs of the surgical site will be obtained using a Canon 50D digital camera body with a Canon 100mm f/2.8 macro lens and a Canon MR-14EX macro ring flash or a similar product. The photographs will be stored in the subject's medical history and chart.
- Concomitant medication changes
- Adverse event assessment

- Subject exit

Figure 3 Appointment flow chart

[figure not shown]

Table 1 Study plan

Visit Number	1	2	3	4	5	6	7
Visit Description	Screening	CBCT	GBR	1 w post GBR	2 w post GBR	4w post GBR	CBCT- 6 m post GBR
Patient Information							
Informed consent	X						
Patient demographics	X						
Medical/surgical history	X						
Oral examination	X						
Inclusion/exclusion criteria	X						
Radiographic examination	X						
CBCT		X					X
Clinical photography			X	X	X	X	X
Randomization			X				
Guided bone regeneration			X				
Suture removal					X		
CBCT measurements	Bone dimensions		X				X
	BMD		X				X
Inflammation				X	X	X	X
Wound dehiscence, membrane exposure, and infection				X	X	X	X
Post-surgical care instructions			X				
Adverse events/Adverse device effects			X	X	X	X	X
Concomitant medication	X	X	X	X	X	X	X
Subject exit							X

3.2 Rationale and risk/benefit assessment

Possible complications following any oral surgery include thermal sensitivity, flap sloughing, some loss of crestal bone height, abscess formation, infection, pain, swelling, and complications associated with the use of anesthesia. As with any type of surgical therapy, the patient may experience discomfort for a few days.

It is necessary to further define the effects of different grafting materials on clinical outcomes following localized alveolar bone augmentation. This study will employ gold standard methods of evaluation efficacy and safety conforming to that stipulated of the medical, clinical research, and regulatory communities to demonstrate clinical benefit of GUIDOR® barrier membranes with and without bone replacement grafts. The study has been designed to treat a clinical scenario commonly encountered in clinical practice.

There are no additional risks to the patient for participating in the study which he/she would not otherwise encounter with standard guided bone regeneration procedure. The subject would be receiving tests and CBCT if he/she was not participating in this study.

Patients who receive standard guided bone regeneration whether or not participating in this study benefit from an increased alveolar ridge dimension to permit dental implant placement. The public will benefit from the study results which will help to refine the knowledge of bone healing following augmentation with different grafting material. This will help aid clinicians in the selection of materials to optimize their clinical outcomes of treatment. It will also further characterize the effects of GUIDOR® membrane on soft tissue healing while comparing its outcomes to other commonly used barrier membranes. Data acquisition includes minimally invasive collection methods, both before and after the surgical augmentation procedure.

Study selection record

Investigator(s) will keep a record of subjects who were considered for enrollment but were never enrolled (e.g., subject screening log). This information is necessary to establish that the subject population was selected without bias.

Inclusion criteria

For inclusion in the study subjects must fulfill all of the following criteria:

1. Provide written informed consent
2. ≥ 21 years and ≤ 75 years
3. In need of one or more implants replacing missing or non-restorable teeth in the maxilla within region 14 to 24 or the mandible within region 34 to 44
4. Edentulous for at least 6 months at study site
5. A buccal-lingual ridge width at study site of ≤ 4 mm

6. A mesial-distal distance between adjacent teeth at study site at bone level of at least 5 mm
7. A keratinized mid-buccal mucosal thickness of at least 2 mm at study site (measured buccally at MD midline from the mucogingival junction to the projected alveolar ridge crest)
8. Teeth adjacent (mesial and distal) to study site must consist of two stable, natural teeth without signs of periodontal bone loss (> 3 mm) and/or significant soft tissue loss
9. A minimum of twenty teeth in good repair

Exclusion criteria

Any of the following is regarded as a criterion for exclusion from the study:

1. Insufficient interocclusal distance for future dental implant placement and restoration
2. More than 3 mm vertical bone loss at study site as measured from the mid-buccal crest of bone on the adjacent teeth
3. Previous site development (soft and/or bone tissue) performed at the study site
4. Untreated rampant caries and uncontrolled periodontal disease
5. A history within the last 6 months of the daily use of any tobacco products besides cigarettes (smokeless chewing tobacco, e-cigarette, pipe or cigar smoking), or of smoking more than 10 cigarettes per day.
6. Current alcohol dependency, alcohol abuse or chemical dependency based on DSM-IV Criteria or drug abuse
7. Subjects having uncontrolled endocrine-induced diseases (e.g. uncontrolled diabetes mellitus and hyperparathyroidism)
8. Systemic or local disease or condition that would compromise post-operative healing and/or osseointegration
9. Use of any substance or medication that will influence bone metabolism (e.g. intravenous bisphosphonates)
10. Need for systemic corticosteroids or any other medication that would influence post-operative healing and/or osseointegration
11. History of radiation in the head and neck region > 30 Gy
12. Subject reports pregnancy or is nursing at the time of enrollment

13. Unable or unwilling to return for follow-up visits for a period of 6 months
14. Unlikely to be able to comply with study procedures according to Investigators judgement
15. Previous enrollment or randomization of treatment in the present study
16. Participation in another clinical trial within 30 days of enrollment

Restrictions

Subjects will be advised of the following restrictions during the study period:

- To avoid disruption of wound healing during the initial study period the subject should have a restricted diet for at least 14 days (printed instructions will be distributed to the subjects at Visit 3 per institutional standard of care)
- For current smokers, no more than 10 cigarettes per day are allowed

Discontinuation of subjects from treatment or assessment

3.2.1.1 Criteria for discontinuation

Subjects may be discontinued from study treatment and assessments at any time. Specific reasons for discontinuing a subject from this study are:

- Voluntary discontinuation by the subject who is at any time free to discontinue his/her participation in the study, without prejudice to further treatment
- Safety reasons as judged by the investigator
- Severe non-compliance to protocol as judged by the investigator
- Subject received further dental therapy on study site or adjacent teeth without consent of investigator (e.g. new crown, periodontal surgery, or orthodontics on adjacent teeth)
- Subject lost to follow-up

3.2.1.2 Procedures for discontinuation

Subjects who discontinue should always be asked about the reason(s) for their discontinuation and the presence of any AEs or ADEs. If possible, they should be seen and assessed by an investigator(s). Ongoing AEs and ADEs should be followed up.

A subject will be classified as lost to follow up only if, he/she has failed to return to the required study visits and his/her dental status remains unknown, despite 3 documented attempts to contact the subject via telephone, fax, email, and certified letter.

3.2.1.3 Procedures for handling incorrect enrolled subjects

Subjects not meeting the inclusion/exclusion criteria for a study should not be enrolled into the study. If a subject is enrolled who does not meet inclusion/exclusion criteria, a protocol deviation will be completed.

3.3 Treatments

Identity of investigational product and comparators

All components are commercially available.

GUIDOR® barrier membranes are made of polylactic acid with a citric acid ester. It is double-layered; the external layer has large rectangular perforations which face the overlying soft tissues and permit connective tissue infiltration, while the inner layer has small circular perforations which face bone and inhibit fibrous tissue ingrowth. It maintains its barrier function for 6 weeks, with complete resorption occurring by 6 months. Available membrane dimensions include 15 mm x 20 mm, 20 mm x 28 mm, and 30 mm x 40 mm. The membrane is provided in a transparent plastic tray in a sealed aluminium pouch. It comes sterilized via e-beam.

Bio-Gide® barrier membranes are made from non-cross-linked type I/type III porcine collagen. It consists of a dense outer layer that inhibits fibrous tissue ingrowth and a rough, fibrous side that helps with clot stabilization and permits osteoblast cell attachment. Resorption occurs over a period of 24 weeks. Available membrane dimensions include 13 mm x 25 mm, 25 mm x 25 mm, and 40 mm x 50 mm. The membrane is provided in transparent plastic tray in a double blister pack. It comes sterilized via gamma irradiation.

Lifenet Health® mineralized cortical freeze-dried particulate bone allograft has a particle size of 250-1000 µm. Available quantities include 0.25 cc, 0.50 cc, 0.70 cc, 1.20 cc, 2.50 cc. It is sterilized via Allowash XG® technology, consisting of rigorous screening and assessment of donor tissues; cleaning with hypotonic solutions and antimicrobial reagents; decontamination, disinfection, and cleaning regimens with hydrogen peroxide and isopropanol alcohol solutions; and terminal sterilization with gamma irradiation. The particulate material comes packaged in a sterile vial in a blister pack.

GORE-TEX® sutures are expanded polytetrafluoroethylene nonabsorbable monofilament sutures. They are available in suture sizes ranging from CV-0 to CV-8. They are an inert material that elicits minimal tissue reaction.

Labeling

All grafting materials will be labeled as follows:

- “Reference number”
- “Lot number”
- “Expiration date”

The reference number and lot numbers will be recorded in clinical records (source data) and eCRF.

Storage

All study products must be kept in a secure place under appropriate storage conditions. A description of the appropriate storage and shipment conditions are specified on the study product label and product information.

3.4 Method of assigning subjects to treatment groups

Subject numbers (subject ID) will be consecutively allocated in series at day of inclusion (Visit 1). Subjects at center 1 will receive numbers starting at 101 and subjects at center 2 will receive numbers starting at 201. Enrollment will continue until 30 subjects at each center have been allocated a subject ID. If a subject discontinues, the subject number will not be reused.

Subjects will be randomized at day of alveolar bone regeneration (Visit 3). At Visit 2 all study sites in all subjects are considered equivalent. The randomization schedule will be generated using a validated computerized randomization system under the responsibility of the investigatory team. The randomization assignment will be concealed via envelope until the surgical date. Randomization will be stratified by center and smoking habit, i.e. each center will have 10 subjects in each group A, B and C, respectively with an equal number of subjects with current tobacco consumption per group. Each subject will be treated according to the treatment code in the envelope. The allocation will be revealed to the clinician only following flap elevation for the alveolar regeneration procedure.

The randomization code envelopes will be stored at each center by designated research staff.

Pre-study, concomitant and post-study treatment(s)

Systemic corticosteroids or any other medication that would compromise post-operative healing and/or bone healing are not allowed.

After surgery, mouth rinsing with 0.12% non-alcohol chlorhexidine rinse will be subscribed according to local routines.

Subjects will be given post-surgical instructions with regards to diet and oral hygiene. Oral hygiene instructions will be given to the subjects at all study visits.

Other medication, which is considered necessary for the subject's safety and well-being, may be given at the discretion of the investigator(s). The administration of all medication (excluding dietary supplements) must be recorded in the appropriate sections of the CRF.

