6.3 Determination of sample size

A sample size of 20 participants per treatment group was selected following power calculations and allowing for 10% patient dropout. A sample size of 18 patients was calculated for the primary outcome variable (horizontal bone changes) with the assumption that the detectable difference would amount to 0.5 mm with a standard deviation of 0.5. The type I error probability was set at 0.05 and the statistical power was set at 80%.

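### Section 3.4 lets the surgeon learn the arm before periosteal release, decortication and grafting, an avoidable route for performance bias

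*Combined protocol and SAP*

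**What the plan says.** **Timing of the reveal.** Section 3.4 gives two statements. The assignment is hidden up to the day of surgery: "The randomization assignment will be concealed via envelope until the surgical date". Within the operation: "The allocation will be revealed to the clinician only following flap elevation for the alveolar regeneration procedure". Neither names the step at which the envelope is opened.

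**Order of surgery.** Section 3.1 (Visit 3, Surgical Procedure) first raises the flap: "A full-thickness mucoperiosteal flap will be elevated and extended to permit access to the edentulous site requiring bone augmentation". Next comes: "Periosteal release with a new #15 blade and bone decortication of the edentulous site with a 1/4 round bur will be completed". Graft and membrane follow: "Bone graft material and barrier membranes will be placed within the confines of the adjacent osseous architecture accordingly". In group A the graft goes in and the membrane then covers it: "Group A: FDBA reconstituted in saline will be used to augment the edentulous site and will be covered by a GUIDOR® membrane". Group C follows the same order with Bio-Gide. Group B receives the GUIDOR membrane without graft.

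**What is left open.** Release and decortication apply to all groups with named instruments, but their extent is not specified. For FDBA, section 3.3 lists pack sizes only: "Available quantities include 0.25 cc, 0.50 cc, 0.70 cc, 1.20 cc, 2.50 cc". No size or volume is assigned. Under Labeling, the same section has reference and lot numbers recorded; volume used is not among the items.

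**Safeguards present.** One masked analyst reads the CBCT images (4.2.1.1.1), and each center is trained in graft handling before the study starts (6.1, Multicenter).

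**The concern.** A surgeon who places visibly different materials must learn the arm at some point. What matters is how many discretionary steps come after that point. Under section 3.4 as written, all steps after flap elevation may do so.

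A vs C is the comparison that bears on the membrane, since both groups receive FDBA. A tendency to place more graft, or to release and decorticate more, under one membrane would appear in the six-month bone dimension as a membrane effect. In A vs B, unequal release or decortication would be added to the effect of the assigned graft.

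Section 2.1 states the expectation that group A is superior, so operators are not neutral on paper. The primary analysis is an unadjusted Wilcoxon test with no covariates (6.1, 6.2). Because graft volume is not listed for recording, an imbalance could not be reliably checked afterwards.

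**Working it through.** **1. Steps against knowledge of the arm (3.1 read with 3.4)**

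| Step, in the order of 3.1 | May the surgeon know the arm? | What is discretionary | Comparison exposed |
|---|---|---|---|
| Incision and flap elevation | No | – | – |
| Periosteal release | Yes | Extent | A vs B, A vs C |
| Decortication | Yes | Extent | A vs B, A vs C |
| FDBA placement | Yes | Quantity, within the spatial limit | A vs C only |
| Membrane placement | Yes, necessarily | Assigned treatment | – |

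In A vs B, graft or no graft is the assigned treatment, so FDBA quantity is not a co-intervention there. By the listed order, graft status is not needed until decortication is done.

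**2. The plan's own figure.** Inputs from 6.3: difference 0.5 mm, SD 0.5, type I error 0.05 (two-sided by 6.1), power 80%.
- Standardized difference = 0.5 / 0.5 = 1.
- Two-sample t-test: n = 16.71 per group.
- Adjusted for the Wilcoxon test: 16.71 × π/3 = 17.50, rounded up to 18.
- 10% dropout: 18 / 0.9 = 20.

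The stated 18 and 20 reproduce. Simulated Wilcoxon power at 18 per group is 80.0% (20,000 runs).

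**3. Sensitivity to an assumed shift.** The documents give no size for the bias, so a range is assumed. The arms are truly equal, with normal data and SD 0.5 mm, but unequal co-interventions move group A by the shift shown. Entries are the proportion of 20,000 simulated trials with a two-sided Wilcoxon p below 0.05 favouring A.

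| Assumed shift (mm) | 18 per group | 20 per group |
|---|---|---|
| 0 | 2.3% | 2.4% |
| 0.1 | 7.7% | 8.3% |
| 0.2 | 19.7% | 22.1% |
| 0.25 | 28.6% | 32.3% |
| 0.3 | 38.2% | 43.0% |

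**4. Illustrative volume arithmetic.** What graft volume corresponds to the design difference, stated in 6.3 as "the detectable difference would amount to 0.5 mm"? Formula: volume = thickness × area, assuming even spread.
- Whole 15 × 20 mm membrane: 300 mm². 0.5 × 300 = 150 mm³ = 0.15 cc.
- Assumed smaller bed of 100 mm²: 0.5 × 100 = 50 mm³ = 0.05 cc.
- If half the graft is assumed to resorb, both double, to 0.30 cc and 0.10 cc.

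The listed packs run from 0.25 to 2.50 cc, a ten-fold range. The calculation gives only an order of magnitude. The 300 mm² is an untrimmed membrane rather than a graft bed, the 100 mm² is assumed, and the outcome is the position of the facial plate relative to a reference point, not mean thickness.

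**The case against.** The strongest case for the plan has five parts.

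- **Section 3.4 sets only an earliest time.** A center that opens the envelope after decortication complies. This stands. A reader might infer that the protocol orders the reveal before release and decortication; the documents do not say so. They permit it, and that is the defect.
- **Graft bulk is not unconstrained.** Section 3.1 keeps graft and membrane within the neighbouring bone contour in every group. This stands as a boundary, but it is not a fill target and leaves room for different amounts inside it.
- **Nothing shows that a bias would occur.** A reader might take the volume arithmetic or the simulation as evidence that A vs C is compromised. They are not: both start from assumed values, and the documents neither state nor quantify how far release, decortication or graft quantity affects ridge width. That graft quantity matters is a plausible premise, since the graft is placed to augment the site whose dimension is measured.
- **Safeguards exist.** Holding the reveal until the flap is raised protects patient selection and flap design. Training harmonizes handling, and masked reading protects measurement. None of them hides the arm during the later steps.
- **A later membrane reveal may not be workable.** Section 3.1 requires implantation according to the Instructions for Use, which are not in the documents. They may call for the membrane to be prepared earlier. A surgeon could also adjust the graft after learning the membrane. This stands, and it makes that part of the remedy conditional.

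**Conclusion.** The point holds as a gap in section 3.4. The allocation may be known from the moment the flap is raised, so the extent of release and decortication (both comparisons) and the quantity of FDBA (A vs C) can be decided with knowledge of the arm. Neither masked CBCT reading nor training removes this.

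Its size is unknown. On the assumptions in the simulation, a shift well below the 0.5 mm design difference would matter: 0.2 mm raises the chance of a false finding in favour of A from about 2.3% to about 20% at 18 per group. That describes the design's sensitivity and does not predict bias. No change in sample size follows.

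Severity is moderate, because the route is avoidable at little cost. Confidence is moderate, because the actual opening step may already be late at one or both centers and the effect of these steps on the outcome is not documented.

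**What to change.** 1. Change section 3.4 so that the envelope is opened only after periosteal release and decortication are complete. This removes knowledge of the arm from both steps in all groups and fits the order already in 3.1.
2. Add a case report form field for the quantity of FDBA placed, and report it by group for A vs C. This records what was done and sets no amount.
3. Where the Instructions for Use of both membranes allow preparation after grafting, use a two-part envelope. The outer part states FDBA or no FDBA and is opened after decortication. For FDBA subjects, the inner part names the membrane and is opened once the graft is placed and its quantity recorded. If the Instructions do not allow this, items 1 and 2 still apply.

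**Cost.** Re-packing 60 envelopes, one form field and, with the two-part envelope, a short intraoperative delay while the membrane is prepared. No additional patients or visits.
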